5.4.4.2. A mattress pad is recommended to prevent skin breakdown."

After the subject is positioned comfortably on the litter, the pressure mapping will begin. The peak interface pressure (the highest average pressure (mm Hg) measured over each

For Protocol Office use only:

Protocol title: NATO Litter: Fluid Immersion System
(FIS) versus Traditional Mattress for Pressure Dispersion
FDG20160005H wAmd5

(investigator names redacted 23 Jan 20)

DGMC Human Research Protocol

body region) will be measured for the occiput, sacrum, bilateral scapula, buttocks and heel areas. The total body surface area exposed to skin interface pressure greater than 30mm Hg will also be measured in centimeters squared (cm²) for each body region. Measures of tissue perfusion using the tcpO₂ in mmHg will be measured for comparison to baseline data. This process will take approximately twenty minutes for each of the four iterations. An additional 30 minutes is required to change the litter and mattress configurations. After baseline data are captured and tcpO₂ measurements are taken with the subject supine on all four litter/mattress combinations, the session is complete. Data from subjects who do not complete all four litter/mattress combinations will be excluded from the analysis. An estimated 25% attrition rate is factored into this study to ensure that 43 completed data sets are obtained.

6.5. Risks/Benefits:

- There is a potential risk of injury from falling off the litter while attempting to mount or dismount. This risk will be minimized by having a member of the research staff present whenever a subject is on the litter. Staff will be available to assist participants on and off the litter. A step stool will also be available to assist participants in safely mounting and dismounting the litter.
- There is also a potential risk of skin reaction to the adhesive which will hold the transcutaneous oxygenation transducers in place. If a participant shows signs and/or symptoms of skin irritation from the adhesive (redness, itching, rash or hives), the adhesive will be removed and the participant will be encouraged to see their primary care provider if the signs and/or symptoms do not quickly resolve or becomes worse after the adhesive is removed. If the participant's initial reaction to the adhesive pads is severe (difficulty breathing, face/lips, throat swelling, loss of consciousness) the subject will be taken to the DGMC Emergency Department for treatment.
- There is a potential risk of superficial burn from the tcpO₂ transducers. They are heated to 44 degrees Celsius which is 111.2 degrees Fahrenheit. If a participant shows signs and/or symptoms of skin irritation (redness) or complains of burning, stinging or discomfort in the area of the transducers, the transducers will be removed and the participant will be encouraged to see their primary care provider if the signs and or symptoms do not quickly resolve or become worse. If the participant needs immediate medical assistance, they will be taken to the DGMC emergency department for treatment.
- There is no anticipated individual benefit to subjects attributed to participation in this study. Given the economic and overall health impact of pressure ulcer development, a litter mattress system that can help reduce and/or eliminate pressure sore development will be beneficial to military patients in theater and during transport.

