in a hostile and austere environment where care was focused primarily on immediate life-threatening interventions and medical evacuation to a higher level of care. Medical evacuation most likely occurred on a NATO field litter, which can produce peak interface pressures greater than 30 mm Hg over bony prominences³ and limit tissue perfusion³⁵. The combination of poly-trauma, traumatic brain injury, hypoperfusion, sedation, cervical collars, and medical evacuation places injured individuals at high risk for pressure ulcer development early in the care continuum. Finding ways to reduce or eliminate pressure ulcer development is a patient safety/quality of care issue. Interventions to help reduce/eliminate this problem as early in the continuum of care as possible would improve patient safety outcomes and raise quality of care. In the operational setting, that starts with the transport litter.

Purpose:

The purpose of this study is to measure peak skin interface pressures and the total area of the body exposed to skin interface pressures above 30 mm Hg while subjects are in the supine position. Two different support surfaces will be applied to a standard North Atlantic Treaty Organization (NATO) litter (NSN: 6530-01-380-7309) and a Raven 90C Litter (NSN6530-01-432-5114). The support surfaces are the Warrior Evacuation Litter Pad (WELP) and the Dolphin Fluid Immersion System (FIS). These pressure measurements along with transcutaneous oxygenation readings will allow us to determine differences between support surfaces.

This research protocol has one major aim:

To determine the difference in the pressure redistribution qualities between the WELP and the Dolphin FIS

There are also two secondary aims:

1. To determine the difference in the pressure redistribution qualities of the WELP when used as the mattress on the NATO litter and Raven litter.
2. To determine the difference in the pressure redistribution qualities of the Dolphin FIS when used as the mattress on the NATO litter and Raven litter.

6.3. Hypotheses or Research Questions or Objectives:

Research Questions:

1. Is there a significant difference in pressure redistribution qualities between the WELP and Dolphin FIS mattresses on the NATO Litter?
2. Is there a significant difference in the pressure redistribution qualities between the WELP and Dolphin FIS mattresses on the Raven Litter?

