3. Is there a significant difference in the pressure redistribution qualities of the WELP between the NATO and Raven 90C litters?

4. Is there a significant difference in the pressure redistribution qualities of the Dolphin FIS mattress between the NATO and Raven litters?

Hypotheses:

1. Pressure redistribution qualities will be greater for subjects on the Dolphin FIS than the WELP in the supine position.

2. There is a difference in pressure distribution between men and women, given BMI level (high, ideal) for subjects on the WELP padded NATO with Raven litters.

3. There is a difference in pressure distribution between men and women, given BMI level (high, ideal) for subjects on the Dolphin FIS padded NATO with Raven litters.

4. There is a difference in pressure redistribution qualities of the WELP for subjects on the NATO and Raven litters.

5. There is a difference in pressure redistribution qualities of the Dolphin FIS for subjects on the NATO and Raven litters.

Outcome measures:

Pressure Redistribution: Peak Pressure Index & Total Surface Area (TSA)

Pressure redistribution qualities will be measured in mmHg using XSensor X3 pressure mapping technology. To minimize the risk of a faulty sensor or false reading over one sensor, the average of eight cells around the region will be recorded and referred to as the Peak Pressure Index (PPI). Peak interface pressure is the highest average pressure (mm Hg) measured over vulnerable bony prominences (occiput, sacrum, and bilateral scapula, buttocks, and heels).

TSA will be measured in centimeters squared (cm²). Vulnerable bony prominences with skin interface pressures exceeding 30 mm Hg will be documented.

Tissue Perfusion: Transcutaneous Oxygenation:

Transcutaneous partial pressures of oxygen (tcpO₂) in millimeters of mercury (mmHg) is non-invasive measurement/monitoring of the skin's surface partial pressure of oxygen. For purposes of this study, tcpO₂ measurements will be captured in the scapula region and expressed in mm Hg. Transcutaneous tissue perfusion has been used as the index of tissue viability by several groups^{44,45,49}. From the early work of Seiler et al. (1997, 1983)^{47,48}, a baseline tcpO₂ value for

For Protocol Office use only:

Protocol title: NATO Litter: Fluid Immersion System
(FIS) versus Traditional Mattress for Pressure Dispersion
FDG20160005H wAmd5

(investigator names redacted 23 Jan 20)

DGMC Human Research Protocol

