Healthy adults with authorized access to Travis AFB will be offered the opportunity to participate in this study. After the consenting process is completed, subjects will be

For Protocol Office use only:

Protocol title: NATO Litter: Fluid Immersion System
(FIS) versus Traditional Mattress for Pressure Dispersion
FDG20160005H wAmd5

(investigator names redacted 23 Jan 20)

DGMC Human Research Protocol

scheduled for study participation. If time allows, the subject may be able to participate directly after completing the consent process. The subject will be assigned an identification (ID) number which will be annotated on the consent form and all of the data collection documents. The subject's name will only appear on the study consent form. All other study documents and data collection forms will only have the subject's ID number and no other personally identifiable information (PII). Subjects will be asked to wear a nonrestrictive single layer of garments for the study. They will be given a hospital gown to wear over the upper body. This will allow the study staff easy access to the subject's back for application of the transcutaneous oxygenation transducers. Females will not be required to remove their bra. Subjects will be asked their age and have their height and weight measured by a study team member. They will also be asked their litter and mattress preferences at the end of the study. The study portion should take approximately two hours to complete and can be broken into segments for multiple visits if necessary to accommodate a subjects schedule.

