6.6. Subject Population

Form Revised as of 14 Apr 14

G:\60MDG\SGSE\4. SGSE - Clinical Research\IRB Folder\IRB\Templates
and Forms\Master Protocol Office Forms (Do not delete)\Human

Page 11 of 24

For Protocol Office use only:

Protocol title: NATO Litter: Fluid Immersion System
(FIS) versus Traditional Mattress for Pressure Dispersion
FDG20160005H wAmd5

(investigator names redacted 23 Jan 20)

DGMC Human Research Protocol

Age Range: ≥ 18 y/o Children (≤ 18)

Sex: Male Female

Vulnerable Population: No Yes (explain)

Number of Subjects:

- Total Number of Subjects (nation-wide/study-wide): 43
- Number of Subjects Planned for DGMC: 43
- Number of Subjects Planned for (Specify Institution): N/A

Statistical tests will be 2-tailed with a significance level of 0.05. A 25% attrition rate is expected. A total of 53 subjects will be recruited in order to obtain 43 evaluable subjects with complete data sets.

Inclusion/Exclusion Criteria:

Inclusion:

- Adults over the age of 18 years with lawful access to Travis AFB.

Exclusion:

- Orthopedic or neurological conditions that prevent a subject from lying flat (supine) without any pillows for head, neck, or lumbar support
- Medical conditions (such as an uncontrollable tremor or twitch) that prevent a subject from staying still for the required periods of time (20 minute increments).
- Pregnancy
- Inability to ambulate unassisted, unstable gait (presenting increased fall risk)
- Extremity prosthetics (hand/arm or foot/leg)
- Height greater than 72 inches (6 feet) - exceeds length of the litter & mattress surfaces
- Body weight greater than 300 lbs

For Protocol Office use only:

Protocol title: NATO Litter: Fluid Immersion System
(FIS) versus Traditional Mattress for Pressure Dispersion
FDG20160005H wAmd5

(investigator names redacted 23 Jan 20)

DGMC Human Research Protocol

- Subjects who find it difficult, uncomfortable or impossible to remain still for the necessary study time durations (20 minute increments) on the relatively narrow litter surfaces will be removed from the study.
- Subject does not speak or understand the English language

Recruitment:

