Underweight = <18.5

Normal weight = 18.5–24.9

Overweight = 25–29.9

Obesity = BMI of 30 or greater

Ideal = 18.5-24.9

High = 25 or greater

This is a cross-factor design that will use a Repeated Measures Analysis of Variance (ANOVA) model to examine the effects of within and between factors. Mean change in tcpO₂ (mmHg), LDP pressure units, surface area (cm²) will be computed. All analyses will be done using STATA v 13.0 (College Station, TX).

Source of Research Material per Participant:

| Source of Research Material per Participant | Standard Care | Research Driven |
|--|---------------|-----------------|
| Demographic Data | 0 | 1 |
| Age in years (89+ for anyone over 89 years of age) | 0 | 1 |
| Gender – Male or Female | 0 | 1 |
| Body Mass Index (BMI) | 0 | 1 |
| Height (centimeters/inches) | 0 | 1 |
| Weight (pounds/kilograms) | 0 | 1 |
| Pressure Mapping (mmHg) - NATO Litter (WELP) | 0 | 1 |
| Transcutaneous Oxygenation (TcPO ₂) mmHg | 0 | 4 |
| Pressure Mapping (mmHg) - NATO Litter (FIS) | 0 | 1 |
| Transcutaneous Oxygenation (TcPO ₂) mmHg | 0 | 4 |
| Pressure Mapping (mmHg) – Raven Litter (WELP) | 0 | 1 |
| Transcutaneous Oxygenation (TcPO ₂) mmHg | 0 | 4 |
| Pressure Mapping (mmHg) - Raven Litter (FIS) | 0 | 1 |
| Transcutaneous Oxygenation (TcPO ₂) mmHg | 0 | 4 |
| | | |
| | | |
| | | |
| | | |

7. Conflict of Interest

None

8. Investigation Schedule

Estimated Timeline: IRB approval estimated for May 2016. PI PCS'd and alternate deployed, therefore, anticipated protocol start date Jan 2018 protocol start (need additional equipment, supplies, also requesting additional funding).

| | Jan 2018 Y2Q2 | Y2 Q3 | Y2 Q3 | Y2 Q4 | Y3 Q1 | Y3 Q2 | Y3 Q3 | Y3 Q4 |
|-------------|------------------|-------|-------|-------|-------|-------|-------|-------|
| Recruitment | X | X | X | X | | | | |
| Enrollment | X | X | X | X | X | X | | |

For Protocol Office use only:

Protocol title: NATO Litter: Fluid Immersion System
(FIS) versus Traditional Mattress for Pressure Dispersion
FDG20160005H wAmd5

(investigator names redacted 23 Jan 20)

DGMC Human Research Protocol

| | | | | | | | | |
|----------------------|---|---|---|---|---|---|---|---|
| Data Collection | X | X | X | X | X | X | | |
| Statistical Analysis | | | | | | X | X | |
| Publications/Reports | | | | | | X | X | X |

9. Use of Investigational Drug(s) No Yes

10. Use of Investigational Device(s) No Yes

11. Support Required

CIF Support:

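### Dropping every subject who misses one of the four surfaces discards usable readings; on the stated 53-to-43 path this makes the variance 0 to about 21% larger, with no bias or shortfall shown

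*Combined protocol and SAP*

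**What the plan says.** The exclusion rule is in section 6.4 (Research Design and Methods): "Data from subjects who do not complete all four litter/mattress combinations will be excluded from the analysis". Section 6.6 builds recruitment around it: "A total of 53 subjects will be recruited in order to obtain 43 evaluable subjects with complete data sets". Both sections give 25% as the expected attrition.

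Section 6.8 names the analysis: the design "will use a Repeated Measures Analysis of Variance (ANOVA) model to examine the effects of within and between factors". Neither it nor any other section analyses partial data or plans a sensitivity analysis.

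The questions in section 6.3 are narrower than the rule. Question 1 reads "Is there a significant difference in pressure redistribution qualities between the WELP and Dolphin FIS mattresses on the NATO Litter", and Questions 2-4 have the same two-surface form. Hypothesis 1 compares the mattresses without naming a litter. Hypothesis 2 begins "There is a difference in pressure distribution between men and women, given BMI level (high, ideal) for subjects on the WELP" and goes on to cover both litters; Hypothesis 3 does the same for the Dolphin FIS.

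Three further provisions affect who ends up incomplete:
- Section 6.4: the session "can be broken into segments for multiple visits if necessary to accommodate a subjects schedule".
- Section 6.5: on irritation or discomfort "in the area of the transducers, the transducers will be removed".
- Section 6.6: "Subjects who find it difficult, uncomfortable or impossible to remain still for the necessary study time durations" are removed from the study.

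**The concern.** A repeated-measures analysis that needs all four readings discards everything from a subject who supplied one, two or three. Yet a subject with three surfaces can answer two of the four research questions in full, and one with two surfaces can answer one question in four of the six possible combinations. A mixed model would use those readings, and also single readings through the between-subject information.

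Partial sets are foreseeable. Because the session may be split over visits, a subject can leave with surfaces already recorded. Equally, consent comes first and the session may be scheduled later, so some may leave before any surface. The documents do not say which is more common.

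The rule is also not written per outcome. Section 6.4 treats the session as complete once tcpO₂ has been taken supine on all four combinations, and section 6.6 counts only complete data sets. The natural reading is that a subject whose transducers come off is excluded, and loses valid pressure maps too. At stake is precision already paid for in subjects' time.

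**Working it through.** **Inputs from the documents.** 53 recruited and 43 complete (6.6); 25% attrition (6.4, 6.6); surface order randomised for each subject (6.4).

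**The plan's own figure.** 43 × 1.25 = 53.75, which matches 53 to within rounding; 43 / 0.75 = 57.3 does not. Going from 53 to 43 loses 10 subjects (10/53 = 18.9%). A loss of 25% of 53 is about 13, leaving 40. Both cases are carried below.

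**Ceiling.** If every leaver gave full information, the variance ratio would be 53/43 = 1.233 (10 leavers) or 53/40 = 1.325 (13 leavers).

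**Complete pairs only.** With random order, a leaver holds a given pair with probability 0 after one surface, 1/6 after two and 1/2 after three. Pairs discarded per question:

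| Leaving pattern | 10 leavers (43 complete) | 13 leavers (40 complete) |
|---|---|---|
| All before the first surface | 0 | 0 |
| Half before, rest finish 1-3 evenly | 5 × (0 + 1/6 + 1/2)/3 = 1.1 (+3%) | 6.5 × (2/3)/3 = 1.4 (+4%) |
| All finish three | 10 × 1/2 = 5 (5/43 = +12%) | 13 × 1/2 = 6.5 (6.5/40 = +16%) |

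**Mixed model.** Model: surface mean + period + subject + subject-by-mattress + error. Assumed SDs are 10, 8 and 6 mmHg; none is in the documents. The ratio is c′(Σ X′V⁻¹X)⁻¹c over completers, divided by the same expression over all subjects, averaged over all 24 orders. To show the effect of the assumed correlation, it was repeated with the subject-by-mattress SD at zero, so that all surfaces correlate equally.

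| Pattern, contrast | 10 leavers: SD 8 / SD 0 | 13 leavers: SD 8 / SD 0 |
|---|---|---|
| All before, any contrast | 1.00 / 1.00 | 1.00 / 1.00 |
| Half before, pooled mattress | 1.07 / 1.04 | 1.09 / 1.06 |
| All finish three, pooled mattress | 1.21 / 1.16 | 1.29 / 1.22 |
| All finish three, Questions 1-2 | 1.20 / 1.16 | 1.27 / 1.22 |
| All finish three, Questions 3-4 | 1.13 / 1.16 | 1.18 / 1.22 |

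If all 10 finish exactly one surface, the pooled ratio is about 1.05 with SD 8.

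**In plain units, 10 leavers, SD 8.** The complete-case variance of the pooled contrast is (2 × 64 + 36)/43 = 164/43 = 3.81, an SE of 1.95 mmHg. If all leavers finished three, the mixed model gives 3.81/1.21 = 3.15, an SE of 1.78. In the half-before case the SE ratio is √1.07 = 1.03.

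**Check with estimated variances.** REML simulations comparing a mixed model with the complete-case ANOVA gave 1.08 and 1.10 (half before) and 1.20 and 1.30 (all finish three) for 10 and 13 leavers. Monte Carlo SE was 0.010-0.018. These fits were started at the true variances, so they do not show how easily a real fit would converge.

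**The case against.** The strongest reply is that a pre-specified complete-case analysis of a short crossover in healthy volunteers is defensible, and that recruitment was inflated to deliver 43 complete sets. That stands: if 43 complete, nothing falls short of the plan's own target. It is also true that having all leavers quit after exactly three surfaces is an extreme case, and that leaving before the first surface costs nothing.

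The documents do not support four stronger readings that a reader might infer:
- **A loss of about 30%.** This needs 13 leavers, all leaving after the third surface, an assumed subject-by-mattress SD near 8, and the pooled four-surface contrast. The 53-to-43 path cannot exceed 23.3%.
- **Bias.** Removal for discomfort on the litters could make loss depend on the surface. Nothing in the documents gives its sign or size, and a mixed model would not correct selection driven by readings never captured.
- **Silence about removed transducers.** Section 6.4 ties completion to tcpO₂ on all four combinations, so exclusion is the natural reading. It is strict rather than unstated.
- **Every comparison needs only two surfaces.** That is true of Questions 1-4. Hypothesis 1 can pool all four, and Hypotheses 2-3 span both litters, so a lone reading informs them only through a mixed model.

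The objection that a mixed model is more than a change of wording is fair. With 43 to 53 subjects split by sex and BMI group, it needs a stated small-sample method.

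**Conclusion.** The concern holds as a modest efficiency point. The rule discards readings that bear on the stated questions, and no section justifies it.

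- **53 recruited, 43 complete:** the pooled mattress variance is 0% larger if all leave before the first surface, about 4-7% if half do, and 16-21% if all finish three. For Questions 1-4 the maximum is about 13-20%, or 12% counting complete pairs only.
- **13 leavers, 40 complete:** the pooled maximum is 22-29%.

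These ranges rest on assumed SDs, random order, and loss unrelated to the readings. Neither bias nor a shortfall against 43 is shown.

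**What to change.** Replace the exclusion sentence in section 6.4, and align section 6.8, with text such as:

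> For each outcome, all recorded surface measurements are analysed in a linear mixed model with mattress, litter, mattress × litter, sex, BMI group, the interactions of these needed for Hypotheses 2-3, and period as fixed effects, and random subject and subject-by-mattress effects. Estimation is by REML with Kenward-Roger or Satterthwaite degrees of freedom or, if the software version cannot supply them, a stated small-sample alternative. The subject-by-mattress effect is dropped if its variance is estimated at zero. Questions 1-4 and Hypotheses 1-5 are tested as contrasts. The complete-case repeated-measures ANOVA is a sensitivity analysis.

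Period is added because leavers contribute only early readings. Working per outcome keeps valid pressure maps when tcpO₂ is missing. Record the surface and the reason at each withdrawal.

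This is a cheap improvement: a paragraph of analysis text, two data-sheet fields and slightly more analysis work, with no extra visits or subjects. The downside, which the plan should state, is that the main analysis then relies on missing at random.

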Prior to skin oximetry readings, subjects will be asked to refrain from exercising, smoking and drinking caffeinated beverages for at least two hours before data collection. These readings will be performed using specialized equipment from the DGMC hyperbaric clinic. Bilateral transcutaneous oxygenation will be obtained using a radiometer or Perimed™ instrument and by placing electrochemical transducers bilaterally in the region of the subject's scapula. The transducers and probes will be affixed to the skin after the site has been cleaned. To increase permeability of the skin to oxygen at the measuring sites, transducers will be heated to 44° C (111.2°F). After a calibration period of approximately 10-15 minutes, a constant transcutaneous partial pressure of oxygen will be obtained and recorded onto the patient data sheet. Baseline measurements will then be obtained (about five additional minutes) with the subject sitting upright and no pressure applied to the back.

Next, the subject will be asked to lay supine on the first of four randomly assigned litter mattress combinations. Because the litters will be resting on top of stands, special care will be taken by study team members to ensure subjects safely mount and dismount litters without injury. Subjects will be secured to the litters in accordance with Aeromedical Evacuation Equipment Standards (AFI10-2909, 23 July 2013 pages 73-74).

"5.4.4.1. The patient is placed on the litter, covered with the sheet and blanket as necessary, and secured to the litter with 2 litter straps. The straps are placed mid-thigh and on the upper chest of the patient. Secure the litter straps so the buckles are on the aisle side of the litter, and lay the excess strap flat over the patient. DO NOT tie the excess strap in a knot. Litter straps will be visible for inspection.

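### Section 6.5 foresees reactions to the transducer adhesive, severe ones included, but no eligibility criterion in Section 6.6 screens out a volunteer with a known adhesive reaction

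*Combined protocol and SAP*

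**What the plan says.** Section 6.5 names the hazard: "There is also a potential risk of skin reaction to the adhesive which will hold the transcutaneous oxygenation transducers in place". For local signs, the adhesive comes off and the participant is advised to see primary care if matters do not settle. For a severe reaction the text reads: "difficulty breathing, face/lips, throat swelling, loss of consciousness) the subject will be taken to the DGMC Emergency Department for treatment". The same section adds a second hazard at the same sites: "There is a potential risk of superficial burn from the tcpO₂ transducers". The transducers are heated to 44 °C.

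Section 6.4 (Research Design and Methods) places them over both scapulae. On preparation it says: "The transducers and probes will be affixed to the skin after the site has been cleaned".

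Section 6.6 (Subject Population) has one inclusion criterion: "Adults over the age of 18 years with lawful access to Travis AFB". Its exclusions open with "Orthopedic or neurological conditions that prevent a subject from lying flat (supine) without any pillows for head, neck, or lumbar support". The only item framed as a general medical condition is "Medical conditions (such as an uncontrollable tremor or twitch) that prevent a subject from staying still", which concerns movement.

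**The concern.** The protocol recognises that the adhesive can cause harm, in the worst case a systemic reaction. A person who has already reacted to medical adhesive may well know it and could say so if asked. The visible text never asks. Such a person meets the one inclusion criterion, meets none of the exclusions, and could have adhesive-held transducers fitted over both scapulae.

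What is at stake is participant safety. Section 6.5 states that no individual benefit is expected, so a foreseeable risk that a simple question could reduce deserves that question.

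**Working it through.** No formula or stated figure is involved. The check sets the risk section beside the eligibility list and then looks for screening elsewhere.

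**Step 1: count the exclusions in Section 6.6.**
1. Unable to lie flat, for orthopedic or neurological reasons
2. Medical condition that prevents keeping still
3. Pregnancy
4. Unable to walk unaided, or unstable gait
5. Limb prosthesis
6. Height over 72 inches
7. Weight over 300 lbs
8. Difficulty staying still on the narrow litter
9. No English

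That is nine items. None concerns a reaction to adhesive.

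**Step 2: compare with the other risks named in Section 6.5.**

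| Risk | Preventive measure in 6.5 | Matching exclusion in 6.6 |
|---|---|---|
| Fall from the litter | Staff present and assisting; step stool | Yes: item 4, with fall risk given as the reason |
| Adhesive reaction | None; responses after onset only | None |
| Superficial burn | None; responses after onset only | None |

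The plan's own handling of falls shows that it uses eligibility to prevent a foreseeable harm. It does not do so for the adhesive.

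**Step 3: look for screening elsewhere in the visible text.**
- Section 6.4 has the probe site cleaned. It describes no inspection of the skin and no allergy question. It also lets a subject take part directly after consent if time allows.
- Section 6.7 covers falls, privacy and data security. It says protected health information will not be accessed, so a record check would not reveal an allergy.
- Section 6.8 collects age, race, gender, height and weight. It collects no allergy or skin history.

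Nothing visible closes the gap.

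**Step 4: approximate exposure.** Section 6.4 gives 10 to 15 minutes of calibration, about 5 minutes of baseline, and about 20 minutes on each of four surfaces. If the transducers are worn throughout these periods, measurement time alone is 10 + 5 + (4 × 20) = 95 minutes to 15 + 5 + (4 × 20) = 100 minutes. Time to change litters and mattresses is extra, and the protocol does not say whether the transducers stay on during it.

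**The case against.** **There is no contradiction.** Section 6.5 lists harms and the response to each; Section 6.6 lists who may not enter. A reader might infer that the two sections conflict and must be reconciled. They do not conflict: a risk can be disclosed and managed without a matching exclusion. The list is silent on these volunteers and does not invite them. This objection stands, and the point is an omission only.

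**Screening may occur outside the visible text.** The consent pages were removed before review. The consent text in Section 6.6 has staff discuss the risks, answer questions and set aside at least an hour, so a volunteer aware of an adhesive allergy would probably hear of the hazard. This limits the claim to the protocol text. It does not replace an eligibility criterion, because the eligibility list is present and is where one belongs.

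**The methods describe the subjects as healthy adults.** Section 6.4 does so, but the term is undefined and is not carried into the criteria. An otherwise healthy person can have an adhesive allergy. This objection does little.

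**Damaged skin is not a risk that Section 6.5 names.** A reader might infer that the plan also overlooks its own warning about broken or irritated skin at the probe sites. It gives no such warning; its named skin risks are adhesive reaction and burn. Staff also handle the site when they clean it. A skin check is therefore a sensible extra and not part of the defect.

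**Loss of data is not established.** A reader might infer that a reaction removes the whole subject from the analysis, because Section 6.4 drops anyone who does not complete all four combinations. Removing the adhesive ends tcpO₂, but no text says it ends participation or stops the remaining pressure mapping. The call in Section 6.6 for complete data sets makes exclusion plausible without settling it. The plan also leaves room for 53 − 43 = 10 losses. With no reaction rate in the documents, no loss can be attributed to this cause.

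**Conclusion.** The point holds as a safety omission with a cheap remedy. Section 6.5 foresees adhesive reactions, including severe ones, and gives only responses after onset. None of the nine exclusions in Section 6.6 covers a known reaction, so a volunteer with that history is eligible as written. Falls, by contrast, have a preventive exclusion.

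Neither frequency nor effect on the data can be quantified from the documents, and severe reactions may be rare. The conclusion rests on the visible text and assumes that the removed consent pages contain no screening question; if they do, the remaining step is to carry it into the criteria. The omission gives no reason to doubt the comparison of surfaces or the planned analysis.

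**What to change.** Add a known prior reaction to medical adhesive to the exclusions in Section 6.6, and ask each volunteer about it before the transducers are placed. In Section 6.4, a look at the scapular skin when the site is cleaned is a reasonable addition because of the burn risk.

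The cost is one eligibility line, one screening question and a brief look at the site. The downside is that a few volunteers are turned away. No surface, endpoint or analysis model changes.

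Admitting affected volunteers for pressure mapping alone is not recommended as the rules stand. Without tcpO₂ they could count as incomplete, so that route would first need the completeness rules in Sections 6.4 and 6.6 to be amended.
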